**Agents Intervening against Delirium in Intensive Care Unit (AID-ICU):
An international inception cohort study**

Confidential

This document is confidential and the property of CRIC (Centre for Research in Intensive Care), Copenhagen University Hospital, Rigshospitalet, Denmark.

No part of it may be transmitted, reproduced, published, or used without written authorization from CRIC.

Protocol Synopsis

Title	Agents Intervening against Delirium in Intensive Care Unit (AID-ICU):_An international inception cohort study
Objectives	To describe current use of haloperidol and other pharmacological agents for delirium in critically ill patients admitted to ICU in Denmark, Norway, Sweden, Finland, Netherland, Switzerland, Germany, United Kingdom, Italy, Belgium, Canada, Brazil, Spain and France.
Study Design	An inception Cohort study
Outcomes	Primary outcome measure: Number of patients with delirium intervened with haloperidol. Secondary outcome measures: Number of patients with delirium intervened with antipsychotics other than haloperidol, number of patients with delirium, mortality at 90 days after ICU admission, days alive without coma- and delirium and days alive without mechanically ventilation. In a sub-group of patients included in Denmark cognitive impairment at 6 months will be evaluated.
Study Duration	14-day inception period (Marts 1 st to May 30 th 2016); patients will be followed for the duration of admission in ICU with final follow-up at 90 days (6 month at selected sites).
Number of subjects	N=1000
Population	Acutely ill patients aged 18 years or older admitted to one of the participating ICUs in the inception period.

Contents

1. Investigators and Facilities	4
1.1 Study Location.....	4
1.2 Study Management.....	6
1.3 Principal Investigators.....	6
1.4 Site Investigator.....	6
1.5 Statistician.....	6
1.6 CRIC Research Program Management Committee.....	6
1.7 Additional study supervisors.....	7
1.8 Funding and resources.....	7
2. Introduction and background.....	7
2.1 Background information.....	7
2.2 Study Objectives	8
2.2.1 Aim.....	8
2.2.2 Research Question.....	8
2.2.3 Hypothesis.....	8
3. Study Design.....	8
3.1 Type of study.....	8
4. Method.....	8
4.1 Number of subjects.....	8
4.2 Expected duration of study.....	8
4.3 Primary and secondary outcome measures.....	8
4.3.1 Primary.....	8
4.3.2 Secondary.....	8
5. Recruitment	9
5.1 Eligibility.....	9
5.1.1 Inclusion Criteria.....	9
5.1.2 Exclusion Criteria	10

1.2 Study Management

The Management Committee will manage and coordinate the study centrally. A local research team consisting of a Principal Investigator and a study coordinator will manage and coordinate the study locally. The Principal Investigator has the responsibility for data collection and maintenance of study documentation on site.

1.8 Funding and resources

The AID-ICU research program is funded by Innovation Fond Denmark, the Dept. of Intensive Care Unit, Rigshospitalet and the participating ICUs.

The study is not supported by the industry.

2. Introduction and background

2.1 Background information

The American Clinical Practice Guideline for Adult Intensive Care Unit (ICU) patients in 2002 recommended haloperidol as the therapeutic agent for delirium in critically ill patients, with the requirement of monitoring side effects such as prolongation of QT intervals and arrhythmias¹. However, in the 2013 update of the guidelines this recommendation was changed; haloperidol was no longer recommended for delirium in critically ill patients due to lack of evidence of effect. The same guideline suggests that atypical antipsychotics and continuous IV infusion of dexmedetomidine rather than benzodiazepines is suggested to reduce the duration of delirium in ICU patients with delirium even though these interventions also have low level of evidence. Presently, there are no pharmacologic agents with solid evidence of effect for the treatment of delirium in ICU patients².

Delirium is a complex acute or sub-acute organic mental syndrome characterized by altered level of consciousness, comprehensive cognitive impairment, disorientation, perceptual disturbances, attention impairment, reduced or activated motor activity, disturbed sleep patterns and fluctuating motor and mental performances³. Observed incidence rates of delirium in ICU patients range from 16% to 89%⁴. According to The American Society of Critical Care Medicine the most valid and reliable monitoring tools for routine assessment of delirium is the Confusion Assessment Method for the Intensive Care Unit (CAM-ICU) and Intensive Care Delirium Screening Checklist (ICDSC)².

The risk factors for delirium can be divided into two groups: *non-correctable factors* such as previous delirious episodes, age, dementia, smoking, alcohol and other drug abuse and potentially *correctable factors* such as several categories of medication, acute severe illness, lack of sleep, uneasy environment, and co-morbidities².

Delirium in mechanically ventilated patients is associated with increased 6-month mortality rates, more days on the ventilator and longer stay in ICU and hospital⁵⁻⁷. A meta-analysis assessing clinical outcomes in critically ill patients indicated that delirium was associated with more complications including Acute Respiratory Distress Syndrome (ARDS), nosocomial pneumonia, cardiopulmonary oedema, re-intubation, self-extubation, removal of catheter, and cardiac arrhythmia⁸. After discharge from ICU, patients with delirium report more long-term cognitive impairment, which may last up to 12 months^{9,10}.

In a survey from 2011 in USA, haloperidol was reported to be the most widely used neuroleptic agent for delirium in ICU patients, although prolonged QT intervals were observed¹¹.

Non-pharmacological interventions such as early mobilization have in a randomized clinical trial been suggested to decrease delirium and increase the number of ventilator-free days¹².

In spite of the lack of evidence for haloperidol, widespread use for delirium is likely. Because of the potentially serious adverse reactions, large randomised trials assessing the overall benefit and harm of haloperidol for delirium in ICU are needed. Such trials may be complex to perform and we need more knowledge on the current use of haloperidol in the ICU setting to better design such trials.

2.2 Study Objectives

2.2.1 Aim

To describe and explore current use of haloperidol and other pharmacological interventions for delirium in critically ill patients admitted to ICUs in selected countries¹.

2.2.2 Research Question

Which pharmacologic agents are used for delirium in ICU in 2015 and how are they administered?

2.2.3 Hypothesis

Haloperidol is still widely used and remains the first choice pharmacological intervention for delirium in ICU.

3. Study Design

3.1 Type of study

A multicentre 14-day inception cohort study investigating the pharmacological intervention practices of delirium in acutely ill ICU patients (estimated 50 ICUs in 8 countries). The 14-day study period can be selected by sites from Marts 1st to May 30th 2016.

4. Method

4.1 Number of subjects

We expect to include 1000 acutely ill patients admitted to the participating ICUs.

4.2 Expected duration of study

We will include patients in a 14-day inception period and perform final follow-up at 90 days after ICU admission. A subgroup of conveniently sampled patients will be cognitively assessed at 6 months after ICU admission.

4.3 Primary and secondary outcome measures

4.3.1 Primary

Number of ICU patients with delirium intervened with haloperidol (N05AD01)

(Definition: Patients receiving one or more doses of haloperidol and are described as delirious. Delirium defined as below in secondary outcome 2).

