13. Subtype description of delirium (hypo, hyper or mixed¹⁴)
14. Restrained to the bed (y/n)
15. Treatment with continuous vasopressor or inotropes at any time during this day (noradrenaline (C01CA03), adrenaline (C01CA24), dobutamine (C01CA07), dopamine (C01CA04), milrinone (C01CE02), levosimendan (C01CX08), phenylephrine (C01C A06) or vasopressin (H01BA01))
16. Use of invasive mechanical ventilation (y/n) or use of non-invasive ventilation at any time during this day (y/n)
17. Is the patient sedated at any time during this day (y/n), with continuous infusion of
 - a. Propofol (N01AX10)
 - b. Midazolam (N05CD08)
 - c. Dexmedetomidine (N05CM18) (continues > 18 hours pr./day or continuous > 4 hours between 10 pm – 06 am)
 - d. Other

18. Pain management with intravenous opioid infusion for more than 2 consecutive hours at any time during this day (y/n).
 - a. Remifentanyl (N01AH06)
 - b. Sufentanyl (N01AH03)
 - c. Fentanyl (N01AH01)
 - d. Morphine (N02AA01)
19. Pharmacologic intervention for delirium (first initial dose will be recorded, then the 24 hour accumulated verified administrated dose. Is treatment prescribed as fixed or per need or both)
 - a. Antipsychotics
 - i. Haloperidol (N05AD01) (mg/day) (prophylaxis y/n)(regular dosing mg/day or as needed mg/day)
 - ii. Olanzapine (N05AH03) (mg/day) (prophylaxis y/n)(regular dosing mg/day or as needed mg/day)
 - iii. Quetiapin (N05AH04) (mg/day) (prophylaxis y/n)(regular dosing mg/day or as needed mg/day)
 - b. Anxiolytics
 - i. Benzodiazepine (N05BA) (y/n)
 - ii. Rivastigmin (N06DA03) (y/n)
 - iii. Other (y/n)
 - c. Hypnotics and sleeping pills (y/n) if any of the below.
 - i. Zopiclon (N05CF01)
 - ii. Zolpidem (N05CF02)
 - iii. Triazolam (N05CD05)
 - iv. Lormetazepam (N05CD06)
 - v. Nitrazepam (N05CD02)
 - vi. Chloralhydrate (N05CC01)
 - vii. Melatonin (N05CH01)
 - viii. Promethazine (R06AD02)
 - ix. Other

Day 90 after ICU admission

20. Vital status (dead/alive) (if relevant, date of death)
21. Discharged from ICU (Y/N and date)
22. Discharge from hospital (Y/N and date)

6 month after ICU admission

23. Cognitive impairment assessment with RBANS (40 to 160 points)

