7.1 Sample size estimation

In a case control study with a simple random sampling, and an estimated treatment prevalence of delirious patients treated with haloperidol in the ICU of 13% (preliminary data at Dept. of Intensive Care 4131, Rigshospitalet, Copenhagen from May 2014), inclusion of at least **1000** patients is required to yield a 95% confidence interval of a rate of haloperidol use of 11%-15%. With expected mortality rate of 30% 1000 patients will yield a 95% confidence interval of 23% - 38% for 90-day mortality. Fifty ICUs are estimated to include this sample of patients within 14 days ¹⁵.

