7.3 Statistical plan

The number of patients receiving haloperidol (totally and regularly, as needed and mixed dosing) will be presented as frequencies (% with 95% confidence intervals). Numeric data will be given as medians (interquartile range [IQR]). We will compare differences in baseline characteristics using non-parametric tests between patients who receive haloperidol and patients who do not receive haloperidol. To assess risk factors for the use of haloperidol, we will do multivariate analyses including patient characteristics (age, dialysis, shock and mechanical ventilation and delirium in the first 24 h of admission) and ICU characteristic (university hospital, guidelines for identifying and/or treating delirium and average staff-patient ratio). To assess if haloperidol is an independent predictor of 90-day mortality, we will do multivariate analysis including patient characteristics (age, dialysis, shock and mechanical ventilation and delirium in the first 24 h of admission) and time. We will do exploratory analyses on the interaction between delirium and use of haloperidol and the patient-relevant outcomes measure (mortality, days alive without mechanical ventilation and days alive and out for hospital). All statistical tests will be 2-tailed and $p < .05$ considered statistically significant.

8. Data Handling

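### The primary outcome rule counts haloperidol given as prophylaxis or before delirium, 7.3 does not analyse that outcome, and the precision in 7.1 holds only for a share of all admissions

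*Protocol*

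**What the plan says.** The outcome in Protocol 4.3.1 is titled "Number of ICU patients with delirium intervened with haloperidol (N05AD01"). Its definition is "Patients receiving one or more doses of haloperidol and are described as delirious", with delirium defined as in secondary outcome 2 of 4.3.2. Neither the title nor the definition gives a denominator.

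The daily data in 6.1 item 19 include "Haloperidol (N05AD01) (mg/day) (prophylaxis y/n)(regular dosing mg/day or as needed mg/day"), so prophylactic use was foreseen and is recorded. Neither 4.3.1 nor 7.3 refers to the flag.

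The descriptive analysis in 7.3 reads "The number of patients receiving haloperidol (totally and regularly, as needed and mixed dosing) will be presented as frequencies (% with 95% confidence intervals"). It sets no delirium condition and names no denominator.

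The sample size text in 7.1 starts from an "estimated treatment prevalence of delirious patients treated with haloperidol in the ICU of 13" percent. It then says that the sample "is required to yield a 95% confidence interval of a rate of haloperidol use of 11%-15" percent. The sample is the whole cohort, since 4.1 states "We expect to include 1000 acutely ill patients admitted to the participating ICUs". Section 7.2 likewise takes all acute admissions as the analysis population.

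**The concern.** The aim in 2.2.1 and the hypothesis in 2.2.3 concern haloperidol used for delirium. A rule that asks only for a dose and for delirium, in any order and for any reason, measures co-occurrence. Take a patient given prophylactic haloperidol on day 1 who becomes delirious on day 5 and receives no more. Under 4.3.1 this is a case of delirium treated with haloperidol.

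The planned table in 7.3 does not repair this. It drops the delirium condition, so it reports a different quantity from the primary outcome. The 13% in 7.1 can be read as a share of delirious patients or as a share of all admissions, and these answer different questions. Two analysts could both follow the protocol and report different primary percentages, and the choice could be made after the data are seen.

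**Working it through.** **Inputs**
- Assumed rate p = 0.13, stated 95% interval 11%-15%, N = 1000 (7.1, 4.1).
- Delirium incidence: "Observed incidence rates of delirium in ICU patients range from 16% to 89" percent (2.1). This is a published spread, used here only as a range.

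**Formula:** p ± 1.96 × √(p(1 − p)/n)

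**Step 1: the plan's own figure.** With n = 1000, the half-width is 1.96 × √(0.13 × 0.87/1000) = 0.0208, so the interval is 10.9%-15.1%. The Wilson interval is 11.1%-15.2% and the exact interval 11.0%-15.2%. All agree with the stated 11%-15% after rounding. The figure is therefore correct for a share of all 1000 admissions.

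**Step 2: if 13% is a rate among delirious patients.** The number of delirious patients is 1000 × 0.16 = 160 to 1000 × 0.89 = 890.

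| Delirium share | n | Half-width (points) | 95% interval |
|---|---|---|---|
| 16% | 160 | 5.2 | 7.8%-18.2% |
| 40% (assumed) | 400 | 3.3 | 9.7%-16.3% |
| 89% | 890 | 2.2 | 10.8%-15.2% |

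At the low end the half-width is about 2.5 times that of step 1 (5.2/2.1).

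**Step 3: if 13% is a share of all admissions.** Then 130 of 1000 patients are delirious and received haloperidol. The rate among delirious patients would be 130/160 = 81% at one end of the range and 130/890 = 15% at the other. The same 13% fits very different answers to the study question.

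**Step 4: the numerators side by side**
- 4.3.1: any haloperidol, and delirium; no order, no indication.
- 7.1: delirious patients treated where the 13% is introduced, but a rate of haloperidol use where the interval is given.
- 7.3: any haloperidol, with or without delirium.

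**Step 5: effect of prophylactic or pre-delirium doses.** The protocol gives no share of patients whose only haloperidol was of this kind, so no figure can be calculated.

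**The case against.** The strongest reply is that this is a descriptive cohort with no formal test of the primary outcome, that the daily data allow several definitions to be tabulated, and that the rate among delirious patients is the primary count divided by secondary outcome 2. The choice of leading percentage is often left to a statistical analysis plan, which is not at hand. The dosing table in 7.3 could also stand beside the primary outcome without replacing it, and delirium does appear elsewhere in 7.3, as a model covariate and in an exploratory interaction.

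Much of this is fair, and it limits the point in four ways:

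- A reader might infer that 4.3.1, 7.1 and 7.3 use different denominators. That is not shown. 4.3.1 is a count, 7.3 names no denominator, and 7.1 and 7.2 both point to all admissions. The defect is that none is fixed for the primary percentage and that the 13% is ambiguous.
- A reader might infer that never-delirious recipients contaminate the primary outcome. Under 4.3.1 they cannot, because delirium is required. They enter only through the table in 7.3.
- A reader might infer that the primary rate is materially inflated by prophylaxis. The protocol gives nothing from which to size this.
- It is tempting to make timing part of the main definition by counting only doses on or after the first delirium-positive day. However, agitation, non-cooperation and wide-open eyes without contact are part of the delirium definition in 4.3.2 and are not listed as daily items in 6.1 (items 12 to 14). Onset cannot always be dated, and treatment begun before a positive score was charted would be lost.

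The reply does not remove the rest. The wording of 4.3.1 admits prophylactic use that the study itself records separately, and no analysis sentence in 7.3 addresses the quantity defined in 4.3.1. Both are matters of what the protocol states, not detail deferred to another document.

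**Conclusion.** The point holds on three counts. The rule in 4.3.1 does not require haloperidol to be given for delirium or after its onset, and it ignores the available prophylaxis flag. Section 7.3 reports all recipients and so does not analyse the 4.3.1 quantity. The interval in 7.1 is right for a share of all 1000 admissions, but not for a rate among delirious patients. On that reading, with p held at 13%, the half-width is 2.2 to 5.2 points, against about 2 as stated.

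That range rests on the 16%-89% spread in 2.1 applying to this cohort. It is not the study's own forecast, so the extremes are bounds and not expectations. The direction of the numerator problem is clear: the rule can only add patients who were not treated for delirium. Its size is unknown.

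**What to change.** - **4.3.1:** count patients with delirium who have at least one haloperidol dose not flagged as prophylaxis in item 19. Report patients with prophylactic use only separately.
- **Sensitivity analysis:** restrict the numerator to doses on or after the first recorded delirium-positive day, and note that not every sign in the delirium definition is a listed daily item.
- **7.3:** report the 4.3.1 numerator with a 95% confidence interval over patients with delirium (secondary outcome 2), and also over all admissions. Keep the dosing table for all recipients as a separate description.
- **7.1:** state which denominator the 13% has, and give the precision for the expected number of delirious patients.

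The cost is protocol wording and a little more analysis. The main definition needs no new data, since the flag and the daily doses are already collected. The stated precision becomes wider for the delirious denominator.

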4.3.2 Secondary

1. Number of ICU patients with delirium intervened with other antipsychotics than haloperidol
(Definition: Patients receiving one or more doses of 2nd generation anti-psychotics² including olanzapin (N05AH03), rivastigmin (N06DA03), risperidon (N05AX08) and quetiapine (N05AH04),

¹ Denmark, Norway, Sweden, Finland, Netherland, Switzerland, Germany, United Kingdom, Belgium, Spain, Italy, Canada, Brazil and France

AND described as delirious (see definition in secondary outcome 2. Number of patient with delirium)

2. Number of patients with delirium

(Definitions: ICU documented CAM-ICU positive or ICDSC ≥ 4 points (0-8 points) or DOS >3 points (0-13/day points), ICD-10 code (DF05, DF050, DF05), or agitated and/or non-cooperative and/or eyes open wide with no contact (Glasgow Coma Score (GCS) > 7) or restrained to the bed).

3. Mortality at 90 days

(Definition: Death within 90 days of ICU admission)

4. Days alive in ICU without coma and/or delirium

(Definition Coma: Number of calendar days the patient is alive without coma in the period from ICU admission to discharge. Coma defined as RASS (Richmond Agitation Sedation Score) score -3 to -5, Ramsey sedation score 4 to 6, MASS (Motor Activity assessment Scale) 1 to 0 and GCS < 8 . Delirium Definition: Number of calendar days the patient is alive without delirium in the period from ICU admission to discharge. Delirium defined as above in secondary outcome 2. All assessments in a 24 hour period need to be negative for a patient to be assessed delirium-free).

5. Days alive without mechanical ventilation and days alive out of hospital (ICU) in a 90-day period

(Definition: Patient treated with mechanical ventilation either endotracheal intubated or tracheostomy, on controlled or spontaneous mode or patient treated with continuous non-invasive ventilation (NIV) for more than 1 hour. Number of days without a ventilator is registered every 24 hours; every new day at 6 AM is registered as one day. If a patient is re-intubated/or started NIV within 24 hours it will be registered as a full day of mechanical ventilation.

Definition: Number of days alive after discharge from the hospital (ICU), the day of discharge do not count, but from the next day at 6 AM).

6. Rate of cognitive impairment at 6 months after ICU discharge (only in Denmark)

(Definition: Repeatable Battery for the Assessment of Neuropsychological Status (RBANS)¹³ is a comprehensive and validated neuro-psychometric battery for the evaluation of global cognition, including individual domains of immediate and delayed memory, attention, visuospatial construction, and language. RBANS scale ranging from 40 to 160, with lower scores indicating worse performance. With a population age-adjusted mean [\pm SD] of 100 ± 15 (a scale ranging from 40 to 160, with lower scores indicating worse performance))¹⁰.

5. Recruitment

Potential patients will be identified and recruited in participating ICUs by the local investigators.

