5.1 Eligibility

5.1.1 Inclusion Criteria

All adult (age ≥ 18 years) patients admitted acutely to one of the participating ICUs during the 14-day inception period.

² amisulprid (N05AL05), aripiprazol (N05AX12), asenapin (N05AH05), clozapin (N05AH02), lurasidon (N05AE05), olanzapin (N05AH03), paliperidon (N05AX13), quetiapin (N05AH04), risperidon (N05AX08), sertindol (N05AE03), ziprasidon (N05AE04).

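### Secondary outcome 1 counts rivastigmine, which its own drug list omits, and the daily variables cover only 2 of the 11 drugs on that list, so the outcome cannot be derived as defined

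*Protocol*

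**What the plan says.** Three places in the protocol bear on this outcome.

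- **Section 4.3.2, outcome 1.** The title is "Number of ICU patients with delirium intervened with other antipsychotics than haloperidol". The definition requires delirium plus at least one dose of a second-generation antipsychotic, "including olanzapin (N05AH03), rivastigmin (N06DA03), risperidon (N05AX08) and quetiapine (N05AH04".
- **Footnote 2.** It is attached to the drug class in that definition and printed below section 5.1.1. It begins "amisulprid (N05AL05), aripiprazol (N05AX12), asenapin (N05AH05), clozapin (N05AH02), lurasidon (N05AE05), olanzapin (N05AH03), paliperidon (N05AX13", continues with quetiapine, and ends "risperidon (N05AX08), sertindol (N05AE03), ziprasidon (N05AE04". That makes 11 agents, all with codes beginning N05A. Rivastigmine (N06DA03) is not among them.
- **Section 6.1, daily item 19.** Block 19a (antipsychotics) has three entries: haloperidol, olanzapine and, last, "Quetiapin (N05AH04) (mg/day) (prophylaxis y/n)(regular dosing mg/day or as needed mg/day". Block 19b (anxiolytics) contains "Rivastigmin (N06DA03) (y/n". Blocks 19b and 19c (hypnotics) each end with a catch-all line; block 19a does not.

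Baseline item 7 in the same section records antipsychotics as the whole class N05A, but only for use before admission.

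**The concern.** An outcome that counts users of a drug class needs one list of drugs, and the data collected must identify each drug on it. Here the definition, its footnote and the daily variables give three different lists.

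There are two separate problems. The first is classification: the definition counts a drug that the footnote leaves out and that the daily list treats as an anxiolytic. The second is capture: most of the footnote's drugs, including one named in the definition itself, have no place to be recorded during the ICU stay. An analysis plan could settle the first. It cannot settle the second if the data were never entered.

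At stake is the reported frequency of non-haloperidol antipsychotic use, in a study whose aim (section 2.2.1) is to describe which agents are used for delirium.

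**Working it through.** No sample size or power figure is involved. The check compares three lists by ATC code: agents named in outcome 1 (section 4.3.2), footnote 2, and agents with their own entry in item 19 (section 6.1).

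| Agent | Named in outcome 1 | In footnote 2 | Own entry in item 19 |
|---|---|---|---|
| Olanzapine (N05AH03) | yes | yes | yes, 19a |
| Quetiapine (N05AH04) | yes | yes | yes, 19a |
| Risperidone (N05AX08) | yes | yes | no |
| Rivastigmine (N06DA03) | yes | no | yes, 19b (anxiolytics), y/n |
| Amisulpride (N05AL05) | no | yes | no |
| Aripiprazole (N05AX12) | no | yes | no |
| Asenapine (N05AH05) | no | yes | no |
| Clozapine (N05AH02) | no | yes | no |
| Lurasidone (N05AE05) | no | yes | no |
| Paliperidone (N05AX13) | no | yes | no |
| Sertindole (N05AE03) | no | yes | no |
| Ziprasidone (N05AE04) | no | yes | no |

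Counts:

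- Named agents with an entry: 3 of 4. The exception is risperidone.
- Named agents absent from footnote 2: 1 of 4, rivastigmine.
- Footnote 2 agents with an entry: 2 of 11, so 11 − 2 = 9 have none (risperidone and eight others).
- Definition and footnote combined: 11 + 4 − 3 = 12 agents, of which 3 have an entry.

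The catch-all lines in 19b and 19c do not fill the gap. They sit under other drug classes and, as listed, do not ask for the agent's name.

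Four delirious patients show the effect:

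1. Rivastigmine only: counted by the definition, not by the footnote.
2. Risperidone only: qualifies under both, but cannot be identified from the listed variables.
3. Risperidone and quetiapine: counted, through quetiapine.
4. Ziprasidone only: qualifies under the footnote, but cannot be identified.

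For the direction of the error, take delirious patients only. Let A be the number given rivastigmine but no footnote 2 drug. Let B be the number given an unlisted footnote 2 drug but none of olanzapine, quetiapine or rivastigmine. The listed data yield everyone given olanzapine, quetiapine or rivastigmine.

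- Against footnote 2 as the target: error = A − B.
- Against the definition read as footnote 2 plus rivastigmine: error = −B.

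The protocol gives no figure for A or B. On the first reading the sign is unknown; on the second it is a shortfall of unknown size.

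**The case against.** The best defence has four parts.

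- **Rivastigmine is recorded.** It has its own y/n entry, so the outcome can be tabulated with or without it. This stands: the problem with rivastigmine is one of classification, not of missing data.
- **The form is not shown.** Section 6.1 is a variable list, and section 8.1 says the eCRF is programmed separately, so it may hold more fields. This stands as a limit on the claim, which concerns the protocol's list. The protocol still needs to say what is collected.
- **The source data exist.** Section 8.1 takes data from patient records, so sites could go back for missing drugs. That is true, and it rules out calling the data irrecoverable. It would still mean a second pass through the records at an estimated 50 ICUs.
- **Narrowing a short title is ordinary.** The definition restricts the title to second-generation agents. That is the investigators' choice of scope; it deserves at most a wording note.

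A reader might also infer that the gaps bias the study towards its hypothesis, "Haloperidol is still widely used and remains the first choice pharmacological intervention for delirium in ICU". The documents do not support this. Counting rivastigmine raises the non-haloperidol figure while missing unlisted drugs lowers it, and no usage figures are given to net them. The hypothesis concerns pharmacological interventions in general, not antipsychotics alone, and section 7.3 plans no comparison of haloperidol with outcome 1. Nor can a number of lost patients be stated: it would need usage rates the protocol lacks, it applies only to delirious patients, and those who also received olanzapine or quetiapine are still counted.

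**Conclusion.** The point holds in a limited form. Outcome 1 includes one agent that its own footnote excludes, and the protocol's daily variables cannot identify 9 of the 11 footnote agents, including risperidone, which the definition names. The outcome cannot be derived as defined.

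The size is known in drugs (2 of 11 covered), not in patients. The net direction against the footnote list is unknown. The conclusion assumes that the eCRF follows section 6.1 and that footnote 2 states the intended scope of the drug class. The consequence is limited to one descriptive secondary outcome. The primary outcome rests on haloperidol, which has a full entry. The correction is cheap enough that it should be made.

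**What to change.** Reconcile outcome 1, footnote 2 and item 19 so that they share one list.

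1. In section 4.3.2, remove rivastigmine from outcome 1 and report it separately from its existing y/n entry in item 19b.
2. In item 19a of section 6.1, add an entry for risperidone and a line for any other antipsychotic with the agent specified, recorded in the same way as the present entries.
3. Check that the eCRF matches. If data collection has already begun without these fields, ask sites to complete them from patient records, or state in the report that the outcome covers olanzapine and quetiapine only.

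Made before data collection, the cost is one edited definition and one or two eCRF fields. The investigators' restriction to second-generation agents can stay as it is.
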